7.3 Method of Treatment Assignment

Treatment allocation/randomization will occur centrally using an interactive voice response system / integrated web response system (IVRS/IWRS). There are 2 study treatment arms. Participants will be assigned randomly in a 1:1 ratio to pembrolizumab plus SoC (Arm A) and SoC (Arm B), respectively.

7.3.1 Stratification

Treatment allocation/randomization will be stratified according to the following factors:

- Primary tumor site (oropharynx/oral cavity vs. larynx vs. hypopharynx)
- Tumor Stage III vs. IVA
- PD-L1 status defined by TPS 50% (TPS \geq 50% vs. TPS<50%)

7.4 Blinding

This is an open-label trial; therefore, the Sponsor, investigator and participant will know the study treatment administered.

Imaging and pathology data for the planned study analyses will be centrally reviewed by independent radiologist(s) and pathologist(s), respectively, without knowledge of participant treatment assignment. The participant-level PD-L1 biomarker results will be masked in the database to the investigator (see Section 10.2).

7.5 Preparation/Handling/Storage/Accountability

7.5.1 Dose Preparation

Details on preparation and administration of pembrolizumab are provided in the Pharmacy Manual.

Preparation of cisplatin should follow the local product label (eg, for France see Appendix 7 for the most recent version of the medicines SmPC). The body surface area in m² should be calculated per local guidance.

7.5.2 Handling, Storage and Accountability

The investigator or designee must confirm appropriate temperature conditions have been maintained during transit for all study treatment received and any discrepancies are reported and resolved before use of the study treatment.

Only participants enrolled in the study may receive study treatment and only authorized site staff may supply or administer study treatment. All study treatments must be stored in a secure, environmentally controlled, and monitored (manual or automated) area in accordance with the labeled storage conditions with access limited to the investigator and authorized site staff.

The investigator, institution, or the head of the medical institution (where applicable) is responsible for study treatment accountability, reconciliation, and record maintenance (ie, receipt, reconciliation, and final disposition records).

For all trial sites, the local country Sponsor personnel or designee will provide appropriate documentation that must be completed for drug accountability and return, or local discard and destruction if appropriate. Where local discard and destruction is appropriate, the investigator is responsible for ensuring that a local discard/destruction procedure is documented.

The trial site is responsible for recording the lot number, manufacturer, and expiry date for any locally purchased product as per local guidelines unless otherwise instructed by the Sponsor.

The investigator shall take responsibility for and shall take all steps to maintain appropriate records and ensure appropriate supply, storage, handling, distribution and usage of study treatments in accordance with the protocol and any applicable laws and regulations.

7.6 Treatment Compliance

The total volume of study medication infused will be compared with the total volume prepared to determine compliance with each dose administered.

Interruptions from the protocol specified treatment plan due to medical/surgical events or logistical reasons not related to study therapy (eg, elective surgery, unrelated medical events, participant vacation, and/or holidays) >6 weeks between pembrolizumab doses and/or >12 weeks between pembrolizumab doses for drug-related AEs associated with pembrolizumab exposure (see Section 7.2.1 for dose modification guidelines for drug-related events) require consultation between the investigator and the Sponsor and written documentation of the collaborative decision on participant management.

7.7 Concomitant Therapy

Medications or vaccinations specifically prohibited in the exclusion criteria are not allowed during study treatment through follow-up (refer to Appendix 8 for Germany-specific guidances). If there is a clinical indication for any medication or vaccination specifically prohibited, discontinuation from study therapy may be required. The investigator should discuss any questions regarding this with the Sponsor Clinical Director. The final decision on any supportive therapy or vaccination rests with the investigator and/or the participant's primary physician. However, the decision to continue the participant on study treatment requires the mutual agreement of the investigator, the Sponsor and the participant.

The following are prohibited concomitant therapy or vaccination during the course of the study:

1. Antineoplastic systemic chemotherapy or biological therapy, including prior therapy with an anti-PD-1, anti-PD-L1, or anti-PD-L2 agent or with an agent directed to another co-inhibitory T-cell receptor (eg, CTLA-4, OX-40, CD137).

2. Immunotherapy not specified in this protocol
3. Chemotherapy not specified in this protocol
4. Radiation therapy not specified in this protocol, including prior RT for the HNC under study.
5. Investigational agents other than pembrolizumab, including prior use of investigational agents for the HNC under the study.
6. Live vaccines within 30 days prior to the randomization, while participating in the study and receiving study treatment, and for 3 months after the end of study treatment.
Examples of live vaccines include, but are not limited to, the following: measles, mumps, rubella, chicken pox, yellow fever, rabies, *Bacillus Calmette–Guérin*, and typhoid (oral) vaccine. Seasonal influenza vaccines for injection are generally killed virus vaccines and are allowed. However, intranasal influenza vaccines (eg, *FluMist*[®]) are live attenuated vaccines, and are not allowed. Refer to Appendix 8 for Germany-specific requirements.
Note: Any licensed COVID-19 vaccine (including for Emergency Use) in a particular country is allowed in the study as long as they are mRNA vaccines, replication-incompetent adenoviral vaccines, or inactivated vaccines. These vaccines will be treated just as any other concomitant therapy.
Investigational vaccines (ie, those not licensed or approved for Emergency Use) are not allowed.
7. Systemic glucocorticoids for any purpose other than to modulate symptoms from an AE that is suspected to have an immunologic etiology. The use of physiologic doses of corticosteroids may be approved after consultation with the Sponsor. Note the following:
 - A short course of steroids may be used as concomitant medication for either treatment of an AE or medical condition with Sponsor approval.
 - Inhaled steroids are allowed for management of asthma.
 - Use of prophylactic corticosteroids to avoid allergic reactions (eg, to IV contrast dye) is permitted.
 - Use of steroids for antiemetic purposes is permitted.
 - Use of steroids for premedication for study treatment is permitted.
8. No upfront prophylactic growth factor support with granulocyte-colony stimulating factor is allowed during CRT treatment. However, treatment of neutropenia with granulocyte-colony stimulating factor is allowed, if clinically indicated. Use of erythropoietin is not permitted.

9. During Cisplatin treatment only: Cisplatin is a potentially nephrotoxic drug which can be potentiated by other nephrotoxic agents such as aminoglycoside antibiotics. Use of aminoglycosides (such as streptomycin, dihydrostreptomycin, kanamycin, gentamicin, neomycin, tobramycin, netilmicin, and amikacin) should be administered with caution given the risk of nephrotoxicity. The serum creatinine, blood urea nitrogen, and electrolytes should be monitored carefully when additional nephrotoxic agents are used. Participants receiving cisplatin and other potentially ototoxic drugs such as aminoglycosides should also be closely monitored for signs of ototoxicity. If the administration of aminoglycosides is required, additional audiometric testing may be necessary for further safety monitoring. Please contact the Sponsor if aminoglycosides are administered to a study participant in order to discuss renal management as well as frequency of audiometric assessments. Refer to Appendix 8 for Germany-specific guidance.

Participants who, in the assessment by the investigator, require the use of any of the aforementioned treatments for clinical management should be removed from the study.

All treatments that the investigator considers necessary for a participant's welfare may be administered at the discretion of the investigator in keeping with the community standards of medical care. All concomitant medication will be recorded on the electronic case report form (eCRF) including all prescription, over-the-counter products, herbal supplements, and IV medications and fluids. If changes occur during the study period, documentation of drug dosage, frequency, route, and date should also be included on the eCRF.

All concomitant medications received within 28 days prior to randomization and up to 30 days after the last dose of study treatment should be recorded. Concomitant medications administered 30 days after the last dose of study treatment should be recorded for SAEs and ECIs as defined in Section 9.3.

There are no prohibited therapies in the Post-Treatment Follow-up Visits.

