8 DISCONTINUATION/WITHDRAWAL CRITERIA

8.1 Discontinuation of Study Treatment

Discontinuation of study treatment does not represent withdrawal from the study.

As certain data on clinical events beyond study treatment discontinuation may be important to the study, they must be collected through the participant's last scheduled follow-up, even if the participant has discontinued study treatment. Therefore, all participants who discontinue study treatment prior to completion of the protocol-specified treatment period will still continue to participate in the study as specified in Section 2 - Schedule of Activities and Section 9.1.11 – Withdrawal/Discontinuation.

Participants may discontinue study treatment at any time for any reason or be dropped from the study treatment at the discretion of the investigator should any untoward effect occur. In addition, a participant may be discontinued from study treatment by the investigator or the Sponsor if study treatment is inappropriate, the trial plan is violated, or for administrative and/or other safety reasons. Specific details regarding procedures to be performed at study treatment discontinuation are provided in Section 9.1.11 – Withdrawal/Discontinuation.

A participant must be discontinued from study treatment but continue to be monitored in the study for any of the following reasons:

- The participant or participant's legally acceptable representative requests to discontinue study treatment.
- The participant has a medical condition or personal circumstance, which, in the opinion of the investigator and/or Sponsor, placed the participant at unnecessary risk from continued administration of study treatment.
- The participant has a confirmed positive serum pregnancy test.
- BICR verified radiographic disease progression outlined in Section 9.2.1.4.
 - Exceptions:
 - Participants with no histologic evidence of invasive cancer after definitive biopsy of the progressed lesion will not meet criteria for an event.
 - Radiographic disease progression during the neoadjuvant phase that precludes surgery will be considered an event.
- Any progression or recurrence of any malignancy, or any occurrence of another malignancy that requires active treatment.
- Recurrent Grade 2 pneumonitis.
- Completion of 17 doses of treatments with pembrolizumab.

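### Section 7.7 tells sites to remove from the study any participant who needs a listed treatment, which contradicts the sections that keep such participants in follow-up for EFS and OS

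*Combined protocol and SAP*

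**What the plan says.** Section 7.7 gives two consequences for needing a restricted treatment. Its opening concerns items prohibited in the exclusion criteria. It says "discontinuation from study therapy may be required", and then that "the decision to continue the participant on study treatment requires the mutual agreement of the investigator, the Sponsor and the participant". Its closing sentence follows a nine-item list and says that participants who "require the use of any of the aforementioned treatments for clinical management should be removed from the study".

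Section 8.1 separates the two ideas: "Discontinuation of study treatment does not represent withdrawal from the study", and "all participants who discontinue study treatment prior to completion of the protocol-specified treatment period will still continue to participate in the study". Section 9.10.3.1 keeps those who stop for a reason other than progression on study with their regular assessments. Section 9.10.4 sends those who stop without an event to Safety and Post-Treatment Follow-up. Section 5.1 follows everyone for OS until death, consent withdrawal or study end. Section 8.2 names consent withdrawal as the one ground on which a participant must leave, and ends scheduled visits for those who withdraw.

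Section 10.6.1.1 and Table 13 define the primary EFS analysis. Progression, recurrence and death count whether or not visits were missed or new anticancer therapy was started. Participants without an event are censored at the last disease assessment.

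**The concern.** The closing sentence of 7.7 is an operational instruction, and on its face it takes people out of the study. Every section that deals with discontinuation, withdrawal or follow-up keeps them in. The protocol relies throughout on the difference between study and study treatment, so a site cannot safely guess that one word was meant as the other.

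The primary EFS rule works only if participants are still observed after they stop treatment or start something else. Someone removed before an EFS event would be censored at the last scan before removal. Needing an unplanned treatment may well be related to prognosis, so that censoring could be informative. Survival follow-up could be lost as well. A treatment started after an EFS event costs no EFS data.

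**Working it through.** The plan gives no figure for this point, so the check is mainly a comparison of text, followed by a count of what removal could cost one participant.

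**1. Does the conflict survive either reading of the sentence?**
- *Read as leaving the study.* It contradicts Section 8.1 (all who stop treatment early continue), Sections 9.10.3.1 and 9.10.4 (on study and in follow-up), Section 5.1 (OS follow-up for all) and Section 8.2 (consent withdrawal as the only mandatory ground).
- *Read as leaving study treatment.* It still differs from the opening of 7.7, where stopping is only a possibility and continuing by agreement is open. The two sentences overlap only in part: the opening covers exclusion-criteria items, while the list also contains growth factors, erythropoietin and aminoglycosides.
- *Under either reading*, it reaches uses that the list itself allows. These include steroids as antiemetics, growth factor to treat neutropenia, and aminoglycosides, which under item 9 "should be administered with caution given the risk of nephrotoxicity".

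**2. When can the sentence apply?** Section 7.7 also says: "There are no prohibited therapies in the Post-Treatment Follow-up Visits". The sentence therefore applies mainly during study treatment. Under the Schedule of Activities, Arm B enters post-treatment follow-up when RT ± cisplatin ends. Arm A receives pembrolizumab for about one year in total (Section 9.1.10.1.1). The window is longer in Arm A.

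**3. What follows for EFS if a site treats removal as withdrawal?** Scheduled visits stop (Section 8.2). Later progression or recurrence is not seen on schedule, and the participant is censored at the last disease assessment (Section 10.6.1.1). For someone who starts new anticancer therapy, this resembles the sensitivity rule in Table 13 more than the primary rule.

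**4. Upper limit on scheduled scans missed.** Inputs from Section 9.2.1.2: the first scan is 12 weeks (84 days) after the end of RT ± cisplatin, then every 91 days to the end of Year 3 (day 1095), then every 182 days to the end of Year 5 (day 1826). Assumptions: RT starts 6 weeks after surgery, there are no delays, removal comes before the first scan, and the participant is event-free to Year 5.

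With first scan on day d, scans to Year 3 = floor((1095 − d)/91) + 1. With last such scan on day L, further scans = floor((1826 − L)/182).

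- Arm A, surgery week 6, 6 weeks of RT, end week 18: d = 126 + 84 = 210. (1095 − 210)/91 = 9.7, so 10 scans, L = 1029. (1826 − 1029)/182 = 4.4, so 4 more. Total 14.
- Arm A, end week 20 (7 weeks of RT plus 1 week of cisplatin): d = 140 + 84 = 224. 9.6 gives 10 scans, L = 1043. 4.3 gives 4 more. Total 14.
- Arm B, surgery week 4, end week 16: d = 112 + 84 = 196. 9.9 gives 10 scans, L = 1015. 4.5 gives 4 more. Total 14.
- Arm B, end week 18: d = 210, as in the first case. Total 14.
- Arm B, immediate surgery, end week 12: d = 84 + 84 = 168. 10.2 gives 11 scans, L = 1078. 4.1 gives 4 more. Total 15.

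**5. How many people?** Each 1% of 714 is 7.1 participants, but the documents give no rate at which anyone needs a listed treatment.

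**The case against.** The best reply is that the dedicated sections already settle the matter. Sections 8.1, 8.2, 9.10.3 and 9.10.4 govern discontinuation and exit, and one sentence closing a medication list should not override them. Harm needs a site to follow that sentence over all of these. Section 8.2 is written for participants who withdraw, so applying its loss of visits to someone removed by an investigator is an inference.

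The loss is also softened elsewhere. Section 9.10.3.3 asks for standard-of-care imaging or biopsy from participants who stop efficacy assessments early without an event. The Section 2.4 imaging note and Section 9.1.7 collect such data during survival follow-up. The Table 13 sensitivity analysis already shows EFS with censoring at the last assessment before new anticancer therapy. After new anticancer therapy, imaging is strongly recommended rather than required. The scan count is a ceiling, since imaging ends at an EFS event.

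Most of this stands as a limit on the consequence. It does not remove the contradiction: the sentence is wrong as written under one reading and at odds with 7.7's own opening under the other. The mitigations also presuppose that the participant is still being contacted, which is what the sentence puts in doubt.

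A reader might go further and infer that the primary EFS result is already biased, or that the longer window in Arm A pushes it in a known direction. The documents support neither. They show no removal, no rate of use of listed treatments, and nothing that fixes a direction.

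**Conclusion.** The contradiction is certain on the text and should be fixed. Its effect on EFS and OS is conditional. It depends on a site reading the undefined term removed as withdrawal, for a participant without an EFS event, mainly during study treatment. In that case the participant is censored early, against the intent of the primary analysis, and may be lost for survival too. The size of any bias cannot be derived. The limit per person is 14 scheduled scans (15 in Arm B with immediate surgery), under the assumptions listed above. Participants with a later event would miss fewer.

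**What to change.** Reconcile the passages by rewording the closing sentence of Section 7.7. It should say that any effect on study treatment follows the rules given elsewhere in the protocol. It should also say that the participant stays in the study for disease-status and survival follow-up under Sections 8.1, 9.10.3 and 9.10.4 unless consent is withdrawn. State which list items the sentence covers. Send sites a short memo, and check discontinuation records for anyone taken out of follow-up under this sentence. Section 10.1 says that 714 participants have been enrolled, so that check matters at least as much as the rewording. Where consent allows, follow-up could be resumed.

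Two smaller consistency edits can go with it but are separate matters:
- Section 7.7 says that prohibited items "are not allowed during study treatment through follow-up", yet later lifts all prohibitions at Post-Treatment Follow-up Visits. The Germany text in Appendix 8 limits them to screening and treatment.
- The Section 2.4 footnote is ambiguous about disease follow-up after new anticancer therapy, and should be aligned with the imaging note in the same section and with Section 9.10.4.

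The cost is one sentence, two small edits, a memo and a records check. The visits retained are already in the Schedule of Activities. No dose, prohibited treatment, alpha or sample size changes, and no view is taken on which treatments are prohibited or when study treatment stops.

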Coagulation tests (PT/INR and aPTT/PTT)	-----As Clinically Indicated-----										Any participant receiving anticoagulant therapy should have coagulation tests monitored closely throughout the study. PTT may be performed if the local lab is unable to perform aPTT		
Thyroid Function (TSH)				X				X			X	In case of elevated TSH, to add Free T3 and Free T4. Free T4 should be performed on all participants with an elevated TSH; Free T3 only needs to be performed if it is done as a part of local standard of care. If the Free T3 and Free T4 are not available locally, they can be sent to the central laboratory to be performed (see Laboratory Manual for details). TSH to be tested on Day 1 of every 3 rd cycle (ie, Cycles 2, 5, 8, etc), unless clinically indicated.	
AE/SAE review	-----Continuous Reporting-----										Frequency as per SoC/local guidelines.		
Oral and dental check-up	-----Recommended Every 6 months-----											Follow cisplatin label for ototoxicity management.	
Audiometric Testing	-----As Clinically Indicated-----											If clinically indicated. To be performed at Cycles 5, 9 and 13.	
Fiber optic examination of primary tumor site								X			X		

Post-surgery Treatment 2 Phase (Arm A/Pembrolizumab)												
Study Period	Treatment 2 (adjuvant)										Notes	
Visit Number/Title												
Treatment Cycle	1	2	3	4	5	6	7	10	13	16	19	8-15
Week	1	2	3	4	5	6	7	10	13	16	19	22-43
Scheduled Day(s)	1	8	15	1	8	15	1	1	1	1	1	1
Scheduling Window (Days, unless noted)	±3	±3	±3	±3	±3	±3	±3	±3	±3	±3	±3	±3
Future Biomedical Research/Biomarkers												
Blood for RNA Analysis	X					X						
Blood for Plasma Biomarker Analyses	X					X						
Blood for Serum Biomarker Analyses	X					X						
Blood for ctDNA	X					X*			X	X		

Notes

Participants that discontinue study treatment for reasons other than an event/disease progression will enter post-treatment study follow-up.

Participants who discontinue study treatment due to an event/disease progression will enter Safety and Survival Follow-up.

Upon completion of Treatment 2, participants move into post-treatment follow-up.

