Week	-28 to -1	Treatment randomization	0-4	Surgery	Post-surgery Safety Follow-up	1	2	3	4	5	6	7	Participants that discontinue study treatment for reasons other than an event/disease progression will enter post-treatment study follow-up. Participants who discontinue study treatment due to an event/disease progression will enter Safety and Survival Follow-up. At the end of RT ± cisplatin (Treatment 2), participants in Arm B will enter post-treatment study follow-up. Upon completion of RT ± cisplatin in Treatment 2, participants will enter post-treatment follow-up		
Scheduled Day (s)						1	8	15	1	8	15	1			
Scheduling Window (Days, unless noted)			7-30 days post-surgery			±3	±3	±3	±3	±3	±3	±3			
Patient Reported Outcomes															
EQ-5D-5L						X			X*			X*			
EORTC QLQ-C30						X			X*			X*			
EORTC QLQ-H&N35						X			X*			X*			
Safety Procedures															
Full physical examination including neurological exam and Height*						X			X						

If the participant does not complete the PROs for any reason, the Miss Mode form must be completed to capture the reason the assessment was not performed.

* To be completed in conjunction with RT ± cisplatin treatment prior to treatment administration ePRO assessments should be performed on day RT begins and then repeated during RT treatment on Day 29 ± 3 days. PROs are to be administered by trained site personnel. It is strongly recommended that PROs are completed by participants prior to all procedures/assessments, and in the following order: EQ-5D-5L, EORTC QLQ-C30, EORTC QLQ-H&N35.

To be performed by the investigator or qualified designee. Documented routine neurological exams performed within 6 weeks of randomization are acceptable and do not need to be repeated in Screening.
*Height will be measured at Screening only.

Study Screening, Surgery and Post-surgery Treatment 2 Phases (Arm B/SoC)														
Study Period	Screening	Treatment randomization	Presurgery	Surgery	Post-surgery Safety Follow-up	Treatment 2				Notes				
Visit Number/Title						SoC RT ± cisplatin adjuvant								
Week	0-4		1		1		2	3	4	5	6	7		
Scheduled Day (s)	-28 to -1		7-30 days post-surgery		1		8	15	1	8	15	1		
Scheduling Window (Days, unless noted)					±3		±3	±3	±3	±3	±3	±3		
Directed physical examination			X			X	X	X	X	X	X	X	To be performed by the investigator or qualified designee. For participants receiving cisplatin: directed physical examination to include neurological exam before each dose of cisplatin.	

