2.4 End of Treatment and Follow-up Visits (Arms A and B)

End of Treatment and Follow-up Visits (Arms A and B)										
Study Period	End of Treatment	Post-Treatment Follow-up ^a				Notes				
		Safety FU	Post-Treatment FU		Survival FU					
Visit Number/Title	Discontinuation		Up to end of Year 3							
Treatment Cycle/Day			Years 4-5							
Scheduling Window (Days (unless noted)	At time of Treatment Discontinuation	30 days from last dose +14 days	Every 3 months from last scan ±7 days	Q6M ±14 days	Q12M ±14 days	Every 3 months ±14 days				
Administrative Procedures										
Prior/Concomitant Medication Review	X	X	----If Clinically Indicated---							
Post-study Anticancer Therapy Status						X	By telephone contact in Survival FU. In addition, upon Sponsor request, participants may be contacted for survival status at any time during the course of the study. Participants who do not/will not have a scheduled study visit during the Sponsor-defined time period will be contacted by telephone for their survival status (excluding participants that have had a death event previously recorded). After 5 years, participants will be followed by telephone to monitor survival and anticancer treatment status every 6 months (±1 month) for overall survival and/or other anticancer treatment until consent withdrawal from study, becoming lost to follow-up, death or end of the study, whichever is earlier.			
Survival status	<----->					X				

End of Treatment and Follow-up Visits (Arms A and B)							
Study Period	End of Treatment	Post-Treatment Follow-up ^a				Notes	
Visit Number/Title	Discontinuation	Safety FU	Post-Treatment FU		Survival FU		
Treatment Cycle/Day			Up to end of Year 3	Years 4-5			
Scheduling Window (Days (unless noted)	At time of Treatment Discontinuation	30 days from last dose +14 days	Every 3 months from last scan ±7 days	Q6M ±14 days	Q12M ±14 days	Every 3 months ±14 days	
Efficacy Procedures							

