6.2 Exclusion Criteria

Participants are excluded from the study if any of the following criteria apply:

Medical Conditions

1. Has Stage T4B and/or N3 LA HNSCC and/or distant metastases.

Note: As per the AJCC Cancer Staging Manual, 8th edition, the diagnosis of ENE (eg, N3b disease) requires clear evidence of gross ENE on clinical examination supported by strong radiographic evidence. Chapter 5, Staging Head and Neck Cancers, in the AJCC Cancer Staging Manual, 8th edition, defines criteria for evidence of gross ENE on clinical evaluation.

2. Has cancer outside of the oropharynx, larynx, and hypopharynx or oral cavity, such as nasopharyngeal, sinus, other para-nasal, or other unknown primary HNC.
3. A WOCBP who has a positive pregnancy test within 24 hours (urine) or within 72 hours (serum) before randomization or within 24 hours prior to the start of RT ± cisplatin (see Section 9.5.9.2). If the urine test is positive or cannot be confirmed as negative, a serum pregnancy test will be required. In such cases, the participant must be excluded from participation if the serum pregnancy result is positive.

Prior/Concomitant Therapy

4. Has received prior therapy with an anti-PD-1, anti-PD-L1, or anti-PD-L2 agent or with an agent directed to another co-inhibitory T-cell receptor (eg, CTLA-4, OX-40, CD137).

5. Has received prior radiotherapy treatment or systemic anticancer therapy including investigational agents for the HNC under study prior to randomization/allocation.
Note: Radiation therapy to treat a prior HNC is also grounds for exclusion.

6. Has received a live vaccine within 30 days prior to randomization. Examples of live vaccines include, but are not limited to, the following: measles, mumps, rubella, varicella/zoster (chicken pox), yellow fever, rabies, *Bacillus Calmette–Guérin*, and typhoid vaccine. Seasonal influenza vaccines for injection are generally killed virus vaccines and are allowed; however, intranasal influenza vaccines (eg, FluMis[®] [Influenza Vaccine Live, AstraZeneca]) are live attenuated vaccines and are not allowed.

Refer to Section 7.7 for information on COVID-19 vaccines.

Prior/Concurrent Clinical Study Experience

7. Is currently participating in or has participated in a study of an investigational agent or has used an investigational device within 4 weeks prior to randomization.

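### Section 7.7 gives conflicting stopping times for the live-vaccine ban, and its closing sentence makes no exception for the 3 months after treatment

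*Combined protocol and SAP*

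**What the plan says.** Three statements in Section 7.7 set how long live vaccines are barred.

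- **Item 6** bars them for 30 days before randomization, then "while participating in the study and receiving study treatment, and for 3 months after the end of study treatment".
- **The opening** says "Medications or vaccinations specifically prohibited in the exclusion criteria are not allowed during study treatment through follow-up". Live vaccines come under it through exclusion criterion 6 in Section 6.2: "Has received a live vaccine within 30 days prior to randomization".
- **The closing sentence** says "There are no prohibited therapies in the Post-Treatment Follow-up Visits". It carries no exception and no cross-reference to item 6.

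The header of the numbered list adds a general duration: "The following are prohibited concomitant therapy or vaccination during the course of the study".

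The Schedule of Activities says when post-treatment follow-up begins. For Arm A (Section 2.2): "Upon completion of Treatment 2, participants move into post-treatment follow-up". For Arm B (Section 2.3): "At the end of RT ± cisplatin (Treatment 2), participants in Arm B will enter post-treatment study follow-up". Section 2.4 places the Safety Follow-up visit under the post-treatment follow-up heading, at "30 days from last dose +14 days".

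Appendix 8 covers live vaccines for two countries only. The UK text restates 3 months after the end of study treatment. The German text confines the prohibitions to screening and treatment, and adds 3 months from the last cisplatin dose for Arm B and for participants who stop early after at least one cisplatin dose.

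**The concern.** The three statements govern the same act, giving a live vaccine after study treatment, and cannot all be followed literally. On day 60 after the last dose, item 6 and the opening forbid it, while the closing sentence, read as it stands, permits it. On day 200, item 6 and the closing sentence permit it and the opening forbids it.

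The two errors differ in consequence. The opening is too strict, which costs little. The closing sentence is too permissive: a site relying on it alone could treat the ban as lifted inside the interval that item 6 sets as a safety precaution. What is at stake is participant safety and consistent conduct across sites, not the efficacy analysis.

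**Working it through.** The plan states no figure to reproduce. The check compares the stopping times and then counts the days on which they disagree.

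**Stopping times for live vaccines, with day 0 as the end of study treatment**

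| Text in Section 7.7 | Ban ends |
|---|---|
| Closing sentence | start of post-treatment follow-up |
| Item 6 | 3 months after day 0 |
| Opening | end of follow-up |
| List header | end of the study |

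The last two rows are close in duration, because the course of the study includes follow-up. The header is also general, and items 6, 8 and 9 beneath it set their own limits. The wordings therefore reduce to about three distinct stopping times.

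**Inputs**

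- 3 months = 91 days, the protocol's own conversion (Sections 2.4 and 9.10.3.3).
- Start of follow-up: end of Treatment 2 in Arm A (Section 2.2), end of RT ± cisplatin in Arm B (Section 2.3).
- Safety Follow-up visit: day 30 to day 30 + 14 = 44 (Section 2.4).
- First imaging after RT: 12 weeks ± 7 days, that is 84 ± 7 days, after the end of RT ± cisplatin (Section 2.4).

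**Overlap of item 6 with the phase said to have no prohibitions** = 91 − (day on which follow-up starts)

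- Follow-up starts when treatment ends: 91 − 0 = 91 days, the whole ban.
- Follow-up starts after the Safety Follow-up visit: 91 − 44 = 47 days to 91 − 30 = 61 days.
- Only scheduled visits count, with the Safety visit left out: Arm B's first follow-up imaging falls on days 84 − 7 = 77 to 84 + 7 = 91, still inside the ban. This step applies to Arm B only, where RT ± cisplatin is the last study treatment.

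The conflict is present on every reading of when follow-up starts. Only its length changes.

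**Which rule is intended.** Item 6 and the UK text in Appendix 8 both give 3 months after study treatment. The Document History entry for Amendment 01 describes the same extension, which I use only as evidence of intent. No global text tells a site that item 6 overrides the closing sentence.

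**The case against.** The best defence is that a specific rule governs a general one: item 6 is explicit, and a careful reader would apply it. Section 7.7 also pairs therapy with vaccination as separate things, so therapies in the closing sentence may simply not cover vaccines. This is a fair reading, and it makes actual error unlikely. It does not settle the matter. The section is titled Concomitant Therapy, and it says permitted COVID-19 vaccines are handled like any other concomitant therapy. Even if the reading is accepted, the opening still disagrees with item 6 on how long live vaccines are barred.

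Safeguards also exist. Sites may put questions to the Sponsor Clinical Director, and Section 7.7 leaves the final decision on a vaccination with the investigator or primary physician. SAEs are collected for 90 days after treatment (Section 9.3.1) unless new anticancer therapy starts, so a serious reaction would normally be captured. These points stand and keep the matter minor.

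Three stronger readings are tempting, and the documents do not support them.

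- A reader might infer that anticancer drugs are wrongly barred in follow-up. The opening does say so literally, but Sections 2.4, 5.1, 5.4.1.1.4, 9.10.2 and 9.10.3.3 plainly expect and record such treatment. That clash has little practical effect.
- A reader might infer that this wording causes vaccinations to go unrecorded after about a month. The recording window is set separately, in another paragraph of Section 7.7 and in Section 9.1.5.2. It would be the same if the prohibition were worded perfectly.
- A reader might count four incompatible end-points. The opening and the list header are too close in duration for that.

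**Conclusion.** The point holds as a wording conflict between current safety rules. Section 7.7 gives about three stopping times for live vaccines, and its last word on the subject is an unqualified permission. The overlap is 91 days if follow-up starts when treatment ends, as Sections 2.2 and 2.3 say, and 47 to 61 days if it starts after the Safety Follow-up visit.

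This rests on two assumptions: that 3 months means 91 days, and that therapies can be read to include vaccines. The second is contestable. If it is rejected, only the conflict between the opening and item 6 remains for vaccines.

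The exposure is mainly outside the UK and Germany, which have their own texts. The documents give no rate of live-vaccine use, and few participants are likely to be concerned. EFS, mPR, OS, error control and power are unaffected. The correction is worth making because it is cheap, not because the trial's conclusions depend on it.

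**What to change.** Change two phrases in Section 7.7.

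- **Closing sentence:** *Except for live vaccines, which stay prohibited until 3 months after study treatment ends (item 6; see Appendix 8 for Germany), no therapy is prohibited in Post-Treatment Follow-up.*
- **Opening:** replace the stated duration with *from randomization through the end of study treatment and, for live vaccines, for 3 months thereafter*, keeping the reference to Appendix 8.

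Leave item 6 and the country texts as they are. Leave the list header unchanged too or, if it is edited, use *from randomization through the end of study treatment, unless an item states otherwise*. It should not be cut back to study treatment alone. Arm B has no neoadjuvant therapy and goes to surgery within 4 weeks of randomization (Section 9.10.2.1), and surgery counts as study treatment (Section 10.5.2). A header limited to study treatment could therefore stop barring non-protocol therapy in Arm B between randomization and surgery. Such therapy matters for mPR, because Section 10.6.1.2 classes participants who take it as non-responders.

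The cost is two phrases in the next amendment, or a clarification letter to sites. Design, endpoints and analysis do not change. Section 10.1 reports all 714 participants enrolled, so the change helps only those not yet 3 months past their last study treatment.
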